**Table 4: Guidelines for Treatment Interruption or Discontinuation and Dose Modification**

Toxicity	Management, Monitoring, and Dose Modification	Discontinuation of Drug
	Immediate Actions/Resolution	
Adverse Events		

Lambda AE ≥ Grade 3, considered at least possibly related to study drug and clinically significant, and no specific guidance given below
	
Interrupt dosing and monitor weekly
 
Resolution: If event resolves to ≤ Grade 1 or baseline value, restart dosing at DR1
	
If event does not resolve in 2 weeks (missed 2 consecutive doses of drug) or If event recurs at DR1, discontinue drug

Lonafarnib AE ≥ Grade 3, considered at least possibly related to study drug and clinically significant, and no specific guidance given below
	
Interrupt dosing and monitor weekly
 
Resolution: If event resolves to ≤ Grade 1 or baseline value, restart dosing at DR1
	
If event does not resolve in 2 weeks (missed 14 consecutive doses of drug) or If event recurs at DR1, discontinue drug

Toxicity	Management, Monitoring, and Dose Modification	Discontinuation of Drug
Lambda AE $\geq$ Grade 3, considered at least possibly related to study drug and not clinically significant, and no specific guidance given below	Discuss with medical monitor. Not all Grade 3 AEs will require dose modification.	
Lonafarnib AE $\geq$ Grade 3, considered at least possibly related to study drug and not clinically significant, and no specific guidance given below	Discuss with medical monitor. Not all Grade 3 AEs will require dose modification.	
Lambda Depression	See Table 5 and CTCAE neurologic definitions for mild/moderate/severe depression Interrupt dosing. Obtain psychiatric consult	
Lambda New ocular symptoms: New decrease or loss of vision or other clinically significant ocular sign or symptom	Interrupt dosing. Obtain complete eye examination performed by an ophthalmologist. Discuss further management with the medical monitor prior to restarting therapy.	
Hematologic abnormalities		
Lambda		
ANC		
$\geq 750/\text{mm}^3$	Maintain dose	
$< 750/\text{mm}^3$	Interrupt dosing Resolution: If ANC $> 500/\text{mm}^3$ , restart dosing at DR1	If event does not resolve in 4 weeks (missed 4 consecutive doses) or If event recurs (confirmed) at DR1, discontinue drug
Platelets		
$< 40,000$	Reduce dose to DR1	
$< 25,000$		If event is confirmed, discontinue drug

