Toxicity	Management, Monitoring, and Dose Modification	Discontinuation of Drug
Hepatobiliary abnormalities  Lambda		
ALT/AST/TBILI $\geq$ CTCAE grade 2	Repeat tests within 48-72 hours and monitor weekly. Monitor ALT, AST, TBili, DB, Albumin, PT/INR Involve medical monitor  Resolution: CTCAE <grade 2, return to routine monitoring.	
ALT/AST $\geq$ CTCAE grade 3	Interrupt dosing  Monitor ALT, AST, TBILI, DB, albumin, PT/INR weekly Involve medical monitor  Resolution: If ALT/AST <CTCAE grade 3, restart dosing at DR1 if agreed upon with medical monitor with weekly monitoring for the first 4 weeks. If stable after 4 weeks of monitoring can resume regular per protocol monitoring.	If event does not resolve in 4 weeks (missed 4 consecutive doses) or If event recurs (confirmed) at DR1, discontinue drug
TBILI $\geq$ CTCAE grade 3	Interrupt dosing  Monitor ALT, AST, AP, TBILI, DB, albumin, PT/INR weekly Involve medical monitor  Resolution: If TBILI $\leq$ CTCAE grade 3, restart dosing at DR1 if agreed upon with medical monitor with weekly monitoring for the first 4 weeks. If stable after 4 weeks of monitoring can resume regular per protocol monitoring.	If event does not resolve in 2 weeks (missed 2 consecutive doses) or If event recurs (confirmed) at DR1, discontinue drug
Lonafarnib		
ALT/AST/TBILI $\geq$ CTCAE grade 2	Repeat tests within 48-72 hours and monitor weekly. Monitor ALT, AST, TBili, DBili, Albumin, PT/INR Involve medical monitor  Resolution: CTCAE <grade 2, return to routine monitoring.	
ALT/AST $\geq$ CTCAE grade 3	Interrupt dosing  Monitor ALT, AST, TBILI, DB, albumin, PT/INR weekly Involve medical monitor  Resolution: If ALT/AST <CTCAE grade 3, restart dosing at DR1 if agreed upon with medical monitor with weekly monitoring for the first 4 weeks. If stable after 4 weeks of monitoring can resume regular per protocol monitoring.	If event does not resolve in 2 weeks (missed 14 consecutive doses) or If event recurs (confirmed) at DR1, discontinue drug

Toxicity	Management, Monitoring, and Dose Modification	Discontinuation of Drug

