TBILI $\geq$ CTCAE grade 3	Interrupt dosing  Monitor ALT, AST, AP, TBILI, DB, albumin, PT/INR weekly Involve medical monitor  Resolution: If TBILI <CTCAE grade 3, restart dosing at DR1 if agreed upon with medical monitor with weekly monitoring for the first 4 weeks. If stable after 4 weeks of monitoring can resume regular per protocol monitoring.	If event does not resolve in 2 weeks (missed 14 consecutive doses) or If event recurs (confirmed) at DR1, discontinue drug
Renal function abnormalities ( lonafarnib AND lambda )		
Creatinine clearance < 50 mL/min		Discontinue drug

**In addition to the above rules, all subjects who meet criteria for a treatment related liver event will undergo the following clinical work up:**

- Ultrasound of the liver should be performed, including doppler, for subjects with a bilirubin level greater than 1.5 times baseline
- If clinically feasible, a liver biopsy should be performed.
  - o When a percutaneous biopsy is contraindicated, a transjugular biopsy may be discussed.
- Liver and chemistry labs should be performed weekly (minimally include ALT, AST, bilirubin, INR, alkaline phosphatase, albumin and gamma-GT) until the bilirubin returns to baseline value.
- HBV DNA and HDV RNA should be monitored weekly
- 5 ml of serum plus 5 ml of plasma should be collected for possible later biomarker analysis
- Autoimmune markers (antinuclear antibody [ANA], anti-smooth muscle antibody [anti-SMA], anti-LC1, anti-SLA liver kidney microsome type 1 and type III antibody [anti-LKM1,3]),
- \_C3, C4 and CH50,
- \_Acute viral hepatitis,
  - o Serologies for acute hepatitis A and E (IgM);
  - o PCR for HCV, hepatitis E (stool and blood),
  - o *Cytomegalovirus* (CMV), PCR
  - o *Epstein-Barr virus* (EBV), PCR
  - o Herpes simplex viruses 1 and 2 (HSV), PCR
- \_Review of pre-existing hepatic disease (excluding HBV),

- Review of concomitant medication(s), or herbal medications and substances known to be hepatotoxic, tests for alcohol and acetaminophen and drugs of abuse, if indicated

**Table 5. Scoring of toxicity for dose modification.** Scoring of toxicity from the CTCAE Version 4.03, with modifications for leukocytes, platelets, prothrombin time, partial thromboplastin time, ALT, AST and bilirubin. Normal ranges for values at the NIH Clinical Center are used.

Scoring of toxicity for dose modification						
		Grade				
Adverse Event	Short Name	1	2	3	4	5

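### Table 4's liver restart rules need two repairs: the lambda bilirubin row permits restart at the grade that stopped dosing, and the grade 3 ALT/AST rows leave it open whether weekly tests continue at grade 2

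*Combined protocol and SAP*

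**What the plan says.** All of this is in the hepatobiliary part of Table 4, which has parallel rows for lambda and lonafarnib.

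- **Grade 2 rows (both drugs).** Any ALT, AST or total bilirubin at grade 2 or above calls for a repeat within 48-72 hours, weekly tests and involvement of the medical monitor. The exit is: "Resolution: CTCAE <grade 2, return to routine monitoring".
- **Grade 3 ALT/AST rows (both drugs).** Dosing stops at grade 3 or above. The exit is: "Resolution: If ALT/AST <CTCAE grade 3, restart dosing at DR1 if agreed upon with medical monitor", with weekly tests for the first 4 weeks after restart. Then: "If stable after 4 weeks of monitoring can resume regular per protocol monitoring". A confirmed recurrence at DR1 (lambda 120 µg, lonafarnib 25 mg, Table 3) means permanent discontinuation.
- **Grade 3 bilirubin row, lambda.** Dosing stops at grade 3 or above. The exit is: "Resolution: If TBILI $\leq$ CTCAE grade 3, restart dosing at DR1", again with the medical monitor's agreement.
- **Grade 3 bilirubin row, lonafarnib.** Same trigger, but the exit is: "Resolution: If TBILI <CTCAE grade 3, restart dosing at DR1".
- **Work-up list after Table 4.** For "all subjects who meet criteria for a treatment related liver event", liver and chemistry labs are weekly "until the bilirubin returns to baseline value".

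**The concern.** A stopping rule should have one reading, and its restart threshold should lie below its stopping threshold. The lambda bilirubin row fails the second test as printed, and the ALT/AST rows do not clearly meet the first.

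These rows decide when a patient who has had a grade 3 liver event is given drug again and how closely that patient is then watched. The section on the hazards of lambda names transaminase elevation, in some cases with raised bilirubin, as the drug's main safety finding. The section on the combination says that its risks are not known. Discontinuation after a recurrence at DR1 depends on a test being done, so the test interval sets how much more drug is given before a recurrence is seen.

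The ALT/AST wording also permits an inversion. A patient at grade 2 who never reached grade 3 must be tested weekly. A patient with the same ALT who did reach grade 3 and was re-exposed could be moved to 4-weekly tests.

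**Working it through.** The plan gives no figure to reproduce. The check sets the rows against the grading scale (Table 5) and the visit schedule (Monitoring on Therapy, Table 1).

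**1. Bilirubin.** Table 5 puts grade 3 at above 3.0 and up to 10.0 times the upper limit of normal (ULN), and grade 4 above 10.0 times.

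| Row | Stop when | Restart allowed when | Overlap |
|---|---|---|---|
| Lambda | above 3.0 × ULN | up to 10.0 × ULN | all of grade 3 |
| Lonafarnib | above 3.0 × ULN | up to 3.0 × ULN | none |

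Two consequences follow for lambda. A patient stopped at grade 3 meets the restart condition on the day of stopping. The rule that lambda is discontinued if the event has not resolved in 2 weeks also loses its force for a grade 3 event, because grade 3 already counts as resolved. Both drugs are given together, so the same bilirubin value would hold lonafarnib and release lambda. Nothing in the document explains a looser rule for lambda, which points to a slip of one symbol.

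**2. ALT/AST.** Table 5 grades against the patient's own baseline: grade 2 is above 5 and up to 10 times, grade 3 above 10 and up to 20 times.

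- Stop: above 10 × baseline. Restart allowed: up to 10 × baseline. There is no overlap, but restart at grade 2 is allowed.
- Weekly tests under the grade 2 row: from above 5 × baseline until 5 × or less.
- After 4 weeks at DR1, a patient still between 5 and 10 × baseline is covered by the grade 2 row (weekly) and, if judged stable, also by the release sentence in the grade 3 row (regular visits). Stability is not defined and no grade is attached to it.

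**3. What regular visits mean at that point.** Scheduled visits are weekly only in weeks 1-3. Four weeks after any restart is later than week 4, so the remaining visits are those of weeks 8, 12, 16, 20 and 24.

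- Gap between tests: 28 days instead of 7, and up to 28 + 3 + 3 = 34 days with the ±3-day windows.
- Lambda doses in the gap (weekly): 28/7 = 4 instead of 1.
- Lonafarnib doses in the gap: 28 × 2 = 56 instead of 7 × 2 = 14, assuming twice-daily dosing continues at DR1. Table 3 gives no frequency; once daily would give 28 and 7.

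**4. Does another section settle it?**

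- The section on ALT flares sends on-treatment flares back to Table 4. The 4-weekly interval for grade 2 in Table 6 is for flares after treatment, when no drug is being given.
- The weekly labs in the work-up list end when bilirubin is back at baseline. If bilirubin never rose, that condition is met from the start, so isolated ALT/AST elevation is not held to weekly tests by this list. The triggering liver event is not defined either.
- Unscheduled Visits allows extra tests but does not require them.
- Data and Safety Monitoring provides weekly rounds and a two-weekly outside review. These look at results that exist and set no test interval.
- The medical monitor must agree to the restart. The release sentence does not ask for agreement to end weekly tests.

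**The case against.** The strongest reply is that the ALT/AST rows do not contradict each other. The grade 2 trigger has no exemption for restarted patients, regular monitoring under the protocol includes Table 4 itself, and the release sentence is permissive while the grade 2 row is an instruction. Someone who keeps testing weekly satisfies both. This stands: a reader might infer two orders that cannot both be obeyed, and the documents do not support that. What remains is a permission that a busy site could use, with nothing in the text to stop it.

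A reader might also infer that restarting at grade 2 is a leniency found only in the liver rows, since the default for other drug-related grade 3 events is "If event resolves to ≤ Grade 1 or baseline value, restart dosing at DR1". That goes too far. The default applies only where no specific guidance exists. In the same table, lambda stopped for neutrophils below 750/mm³ may restart above 500/mm³, and platelets below 40,000 lead to dose reduction without interruption. Thresholds specific to each parameter are the table's general design.

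Third, judgement is a stated choice. Table 4 is a set of guidelines, and the section on adverse events and dose modification prefers individual assessment of AST and ALT to fixed cutoffs. It also says that drugs are not restarted unless another cause is found, which may shrink the group further. The work-up list adds weekly HBV DNA and HDV RNA with no bilirubin end point, so some weekly blood sampling may occur, though without a required ALT. These points lower the practical risk and support treating the ALT/AST matter as a clarification.

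For bilirubin, the medical monitor's agreement and the weekly labs until bilirubin is at baseline make an unwise restart less likely. They do not make the printed threshold right.

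**Conclusion.** Two findings of different weight.

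The lambda bilirubin restart threshold is wrong as written. It overlaps the whole of the grade that triggers interruption and disagrees with the lonafarnib row. This rests on a single printed symbol, which should be checked against the approved protocol file.

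The ALT/AST release sentence is an ambiguity worth removing. It permits 28 days between tests instead of 7, or 4 lambda doses instead of 1, in a patient re-exposed after a grade 3 event, still at grade 2, with bilirubin at baseline. It does not require that gap.

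The affected group is likely very small, and its size cannot be estimated from the documents. A reader might try to infer a rate from the one reduced-dose restart in the lambda monotherapy study described in the Background. On the natural reading that patient was one of the three with jaundice, and so probably falls under the weekly labs tied to bilirubin. The documents therefore show no restart clearly due to isolated ALT/AST elevation. Endpoints and sample size are unaffected. The case for change is that it costs little and concerns patient safety.

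**What to change.** 1. In the lambda grade 3 bilirubin row, change the restart condition from at or below grade 3 to below grade 3, matching the lonafarnib row.
2. In the lambda and lonafarnib grade 3 ALT/AST rows, replace the release sentence with: *If ALT and AST are both below grade 2 after 4 weeks of weekly tests, return to the regular visit schedule; otherwise continue weekly tests.*

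That is wording in three table rows. The first change costs no tests. The second costs none if sites already keep such patients on weekly tests.

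Against the permissive reading, the extra tests for one patient restarted at week r are the 20 − r weekly tests in weeks r + 5 to 24, less the scheduled visits in that span:

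- week 4: 16 − 4 = 12
- week 8: 12 − 3 = 9
- week 12: 8 − 2 = 6
- week 16: 4 − 1 = 3
- week 20: 0

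A restart before week 4 could add one or two more (week 2: 18 − 5 = 13). These are ceilings. They need a patient who stays at grade 2 to week 24 while the weekly rule of the grade 2 row goes unused at every visit. The realistic cost is a few liver panels.

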### ***Lambda Inteferon in Chronic HDV Infection***

Lambda has demonstrated in vivo activity against hepatitis D and hepatitis B viruses. In an HBV/HDV-infected human liver chimeric mouse model, Lambda reduced HDV and HBV viremia by 1.2-log and serum HBsAg level by 2.5-fold after 4 weeks of treatment. The 4 weeks of Lambda treatment also decreased intrahepatic genomic/antigenomic HDV RNA by 6.1/2.2-fold and intrahepatic HBV RNA by 8.6-fold in the mice.

In a first-in-humans for HDV, multicenter, phase 2 clinical trial, Lambda interferon monotherapy is currently being explored (NCT:02765802) in New Zealand, Pakistan and Israel. The Lambda Interferon MonoTherapy study (LIMT) study, has completed enrollment and initiation of dosing in 33 patients that are randomized to receive either 120 µg or 180 µg of weekly administered lambda interferon for 48 weeks followed by 24 weeks of post-therapy follow-up. At the AASLD liver meeting in October 2017, the study investigators reported interim results describing that 10 of 33 patients had reached 24 weeks of therapy. 6 of 10 patients were responders, achieving  $\geq 2$  log decline or below the lower limit of quantitation in HDV RNA at week 24 (Figure 9). Preliminary results also demonstrated that lambda interferon had comparable anti-HDV activity to historical peginterferon alpha at 24 weeks of therapy. These preliminary results appear comparable to peginterferon alpha therapy at similar time points where 15 of 91 subjects (16%) achieved HDV RNA negativity by week 8 and 19 of 91 subjects (21%) achieved HDV RNA negativity by week 12 of therapy in the HIDIT-2 clinical trial. Adverse effects have included grade 3 elevations in ALT in 3 patients and jaundice in 3 patients, two of which required permanent drug discontinuation and 1 required temporary interruption and resumption at a reduced dose. Constitutional symptoms were much milder and less frequent than historical data with IFN alfa.

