**Table 3: Dose reduction plan for Lambda/Lonafarnib intolerability**

Assigned Treatment	Starting Dose	Dose Reduction (DR1)
	Dose	Dose
Lambda	180 µg	120 µg
Lonafarnib	50 mg	25 mg

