Acidosis (metabolic or respiratory)	Acidosis	pH < normal, but >7.3	-----	pH <7.3	pH <7.3 with life threatening consequences	Death
Alkaline Phosphatase (U/L)	Alkaline Phosphatase	>ULN – 2.5 X ULN	>2.5 0 5.0 X ULN	>5.0 – 20.0 X ULN	>20.0 X ULN	-----
Bilirubin (hyperbilirubinemia)	Bilirubin	>ULN – 1.5 X ULN	>1.5 – 3.0 X ULN	>3.0 – 10.0 X ULN	>10.0 X ULN	-----
Albumin, serum-low (hypoalbuminemia)	Hypoalbuminemia	<LLN – 3 g/dL <LLN – 30 g/L	<3 – 2 g/dL <30 – 20 g/L	<2 g/dL <20 g/L	-----	Death
AST, SGOT (serum glutamic	AST	>3 – 5 X patient's baseline values	>5-10 X patient's baseline values	>10 – 20 X patient's baseline values	>20 X patient's baseline values	Death

oxaloacetic transaminase)						
ALT, SGPT (serum glutamic pyruvic transaminase)	ALT	>3-5 X patient's baseline values	>5-10 X patient's baseline values	>10 – 20 X patient's baseline values	>20 X patient's baseline values	Death
Pancreatitis	Pancreatitis		Enzyme elevation or radiologic finding only	Severe pain; vomiting; medical intervention indicated (e.g., analgesia, nutritional support)	Life-threatening consequences; urgent intervention indicated	Death

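### Table 4's lambda bilirubin row interrupts dosing at grade 3 or above but permits restart at grade 3 or below, so an unresolved grade 3 value meets both rules

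*Combined protocol and SAP*

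**What the plan says.** Under hepatobiliary abnormalities for lambda, Table 4 has a bilirubin row whose trigger for interrupting dosing is "TBILI $\geq$ CTCAE grade 3". The resolution rule in the same row is "If TBILI $\leq$ CTCAE grade 3, restart dosing at DR1 if agreed upon with medical monitor", with weekly monitoring for the first four weeks. Lambda is stopped for good if the event has not resolved in two weeks, which the row glosses as two missed weekly doses, or if it comes back on the reduced dose: "missed 2 consecutive doses) or If event recurs (confirmed) at DR1, discontinue drug".

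The neighbouring rows are worded differently. The lambda ALT/AST row says "If ALT/AST <CTCAE grade 3, restart dosing at DR1 if agreed upon with medical monitor". The lonafarnib bilirubin row says "If TBILI <CTCAE grade 3, restart dosing at DR1 if agreed upon with medical monitor". The lonafarnib ALT/AST row also uses the strict sign.

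Table 5 gives grade 3 bilirubin as ">3.0 – 10.0 X ULN", with grade 2 just below it (above 1.5 and up to 3 times ULN) and grade 4 above 10 times ULN. Table 3, headed "Dose reduction plan for Lambda/Lonafarnib intolerability", sets the reduced lambda dose at 120 µg.

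**The concern.** A hold-and-restart rule works only if the value that stops the drug cannot also release it. Here it can. A patient whose bilirubin reaches grade 3 and stays there meets the restart condition from the first result onward.

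This matters most for lambda. The Hazards section (item 14) describes transaminase elevations, in some cases with bilirubin rises, as its main safety finding, and says it appears to be associated with decompensation of cirrhosis. In the lambda monotherapy study in HDV, the interim report gave "jaundice in 3 patients, two of which required permanent drug discontinuation". Item 15 of the same section says the risk of the triple combination is not known.

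The rule also bears on an endpoint. The section on patients discontinuing therapy points to Table 4 for the definition of intolerance, and the Primary Safety End Point counts discontinuation as failure to tolerate. Two physicians reading the same row could therefore classify the same patient differently.

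**Working it through.** The plan states no figure to reproduce. The check compares the grades that trigger interruption with those that allow restart.

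**Step 1. The four hepatic interruption rows of Table 4**

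| Row | Interrupt at | Restart at | Time allowed to resolve |
|---|---|---|---|
| Lambda ALT/AST | grade 3 or above | below grade 3 | 4 weeks |
| Lambda bilirubin | grade 3 or above | **grade 3 or below** | 2 weeks |
| Lonafarnib ALT/AST | grade 3 or above | below grade 3 | 2 weeks |
| Lonafarnib bilirubin | grade 3 or above | below grade 3 | 2 weeks |

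Only the lambda bilirubin row departs from the pattern. Its time limit is shorter than that for lambda ALT/AST, which suggests bilirubin was meant to be handled at least as strictly. Table 4's default for related, clinically significant events of grade 3 or more is stricter still: return to grade 1 or baseline.

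**Step 2. Overlap in the lambda bilirubin row**

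- Interruption grades: {3, 4}.
- Restart grades as written: {0, 1, 2, 3}.
- Intersection: {3}, the whole band above 3.0 and up to 10.0 times ULN.
- Restart grades if the sign were strict: {0, 1, 2}. The intersection is then empty.

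**Step 3. What follows for one unchanged grade 3 value**

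- It triggers interruption.
- It meets the written restart criterion.
- Read literally, it already counts as resolved, so the two-week stop would apply only to a value that stays at grade 4.
- If lambda is restarted, the next confirmed grade 3 result can be read as recurrence on the reduced dose, which means permanent discontinuation.
- Under the lonafarnib bilirubin row the same value keeps lonafarnib on hold.

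**Step 4. Size in mg/dL**

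The documents give no ULN for bilirubin. For assumed values:

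| Assumed ULN (mg/dL) | Restart ceiling with strict sign, 3 × ULN | Restart ceiling as written, 10 × ULN |
|---|---|---|
| 1.0 | 3.0 | 10 |
| 1.2 | 3.6 | 12 |
| 1.3 | 3.9 | 13 |

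For context only, exclusion criterion 1 treats bilirubin above 4 mg/dL as a sign of decompensation at entry. The written ceilings are 10/4 = 2.5, 12/4 = 3.0 and 13/4 = 3.25 times that value. It is an entry criterion, not an on-treatment limit.

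**Step 5. Weight of one patient in the safety endpoint**

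With 26 patients, one patient classified one way or the other moves the tolerability rate by 1/26 = 3.8 percentage points.

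**The case against.** The strongest reply is that the row does not operate alone. Restart needs the medical monitor's agreement, is at the reduced dose, and comes with weekly laboratory tests. The section on adverse events and dose modification goes further. It lists any grade 3 or 4 event, and any event the investigator thinks puts the patient at increased risk, as leading to discontinuation. It also bars restart unless another cause is found. An outside monitor reviews data every two weeks. All of this stands, and it makes an unsafe restart less likely. It does not make the row consistent, and the general section adds a further instruction that conflicts with Table 4's interrupt-and-restart scheme.

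A second reply is that the authors meant restart to be possible once a grade 4 value has fallen to grade 3. The row does not say so, and its trigger already covers grade 3. A third is that the sign is a slip, or was misread when the text was extracted. A slip is likely, given the three parallel rows, and is a reason to correct it. Misreading cannot be excluded, but the same text shows the strict sign in the other three rows; the source file will settle it.

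Four stronger readings are tempting and are not supported:

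- *The monitor has no basis to refuse.* Agreement is an unrestricted condition, and the general section supplies grounds for refusal.
- *The two-week stop can be reached only at grade 4.* That is the literal reading, but not the only one. The event is defined as grade 3 or above, so persistent grade 3 can also be read as unresolved, and the two missed doses accrue whenever the monitor withholds agreement.
- *Two or three of the 26 patients would be affected.* This would carry over the jaundice cases from the monotherapy study. That report gives neither bilirubin grade nor duration. The sign matters only if bilirubin is still grade 3 when restart is decided and the monitor then agrees.
- *Patients could enter the trial already at grade 3.* This depends on a ULN that the documents do not give, and may apply to nobody.

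**Conclusion.** The inconsistency is real and rests on the text alone. The lambda bilirubin row both holds and releases the drug across the whole grade 3 band, and it is the only one of the four hepatic interruption rows to do so. On the assumed ULN range of 1.0 to 1.3 mg/dL, the written restart ceiling is 10 to 13 mg/dL where the sibling rows imply 3.0 to 3.9. The safeguards reduce the practical risk without removing the contradiction. The number of patients whose handling would change cannot be estimated from the documents and may be small.

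A reader might also infer that correcting the sign settles how tolerability is scored. It does not. While the general section says any grade 3 or 4 adverse event leads to discontinuation and Table 4 says interrupt and possibly restart, a grade 3 bilirubin can still be handled, and so scored, in two ways.

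**What to change.** In Table 4's lambda bilirubin row, change the restart condition from grade 3 or below to below grade 3, matching the lambda ALT/AST row and both lonafarnib rows. Leave the interruption trigger, the monitor's agreement and the two-week limit as they are. Check the sign against the source file first.

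Separately, reconcile the general statement on grade 3 and 4 events in the section on adverse events and dose modification with Table 4, stating which governs. The lambda neutrophil row deserves a look at the same time: it interrupts below 750/mm³ and restarts above 500/mm³, an overlap of the same kind.

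The edit to the bilirubin row is one symbol. Its cost is that a patient whose bilirubin stays at grade 3 for two weeks stops lambda permanently instead of resuming at 120 µg, and may count as a tolerability failure. Reconciling the general section takes a sentence or two, but requires the sponsor to decide which rule it wants.
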